8.3.2 Direct access to source data and documents

The investigator /institution will allow site trial-related monitoring, audits, IRB/IEC review and regulatory inspections. Direct access must be provided to the CRF and all source documents/data, including progress notes, copies of laboratory and medical test results, which must be available at all times for review by the CRA, auditor and regulatory inspector (e.g., FDA). They may review all CRFs and informed consents. The accuracy of the data will be verified by direct comparison with the source documents described in Section [8.3.1](#). The sponsor will also monitor compliance with the protocol and GCP.

8.3.3 Storage period of records

Trial site(s):

The trial site(s) must retain the source and essential documents (including ISF) according to contract or the local requirements valid at the time of the end of the trial (whatever is longer).

Sponsor:

The sponsor must retain the essential documents according to the sponsor's SOPs.

8.4 EXPEDITED REPORTING OF ADVERSE EVENTS

BI is responsible to fulfil their legal and regulatory reporting obligation in accordance with regulatory requirements.

8.5 STATEMENT OF CONFIDENTIALITY AND PATIENT PRIVACY

Data protection and data security measures are implemented for the collection, storage and processing of patient data in accordance with the principles 7 and 12 of the WHO GCP handbook.

Individual patient data obtained as a result of this trial is considered confidential and disclosure to third parties is prohibited with the following exceptions:

Personalised treatment data may be given to the patient's personal physician or to other appropriate medical personnel responsible for the patient's welfare. Data generated at the site as a result of the trial need to be available for inspection on request by the participating physicians, the sponsor's representatives, by the IRB/IEC and the regulatory authorities.

8.5.1 Collection, storage and future use of biological samples and corresponding data

Not applicable.

8.6 TRIAL MILESTONES

The **start of the trial** is defined as the date when the first patient in the whole trial signs informed consent.

The **end of the trial** is defined as the date of the last visit of the last patient in the whole trial ("Last Patient Completed").

The "**Last Patient Last Treatment**" (LPLT) date is defined as the date on which the last patient in the whole trial is administered the last dose of trial treatment (as scheduled per protocol or prematurely). Individual investigators will be notified of SUSARs occurring with the trial medication until 30 days after LPLT at their site. **Early termination of the trial** is

defined as the premature termination of the trial due to any reason before the end of the trial as specified in this protocol.

Temporary halt of the trial is defined as any unplanned interruption of the trial by the sponsor with the intention to resume it.

Suspension of the trial is defined as an interruption of the trial based on a Health Authority request.

8.7 ADMINISTRATIVE STRUCTURE OF THE TRIAL

The trial is sponsored by Boehringer Ingelheim.

A Coordinating Investigator is responsible to coordinate investigators at the different sites participating in this trial. Tasks and responsibilities are defined in a contract.

An independent external clinical event committee (CEC) will be established to adjudicate centrally and in a blinded fashion events suspected of DKA (for further details see Section [5.2.6.1.4](#)) and hepatic events. The CEC will evaluate whether pre-specified criteria for adjudication endpoints are met. For qualifying events, study sites will be asked to provide relevant source documents generated from any medical evaluations of these events will be requested including laboratory values, histological analysis, results of ultrasound, computed tomography, magnetic resonance imaging, scintigraphy, hospital discharge letters, and medical reports from other physicians. All evaluations will be performed in a blinded fashion. The assessments will be analysed based on empagliflozin data combined from multiple trials (i.e., on project level). The tasks and responsibilities of the CEC will be specified in a charter. The CEC will maintain the adjudication results in writing.

Relevant documentation on the participating (principal) investigators (e.g., their curricula vitae) will be filed in the ISF.

The investigators and trial staff will have access to the BI web portal Clinergize to access documents provided by the sponsor.

BI has appointed a CT Leader, responsible for coordinating all required activities, in order to

- manage the trial in accordance with applicable regulations and internal SOPs,
- direct the clinical trial team in the preparation, conduct, and reporting of the trial,
- ensure appropriate training and information of CT Managers, CRAs, and investigators of Japan.

The organisation of the trial in Japan will be performed by the respective local or regional BI-organisation (Operating Unit, OPU) in accordance with applicable regulations and BI SOPs, or by a CRO with which the responsibilities and tasks will have been agreed and a written contract filed before initiation of the clinical trial.

Data Management and Statistical Evaluation will be done by BI according to BI SOPs.

A central laboratory service and an IRT vendor will be used in this trial. Details will be provided in the IRT manual and Lab manual, available in the ISF.

Tasks and functions assigned in order to organise, manage, and evaluate the trial are defined according to BI SOPs. A list of responsible persons and relevant local information can be found in the ISF.

10. APPENDICES

10.1 GRIP STRENGTH

A Smedley-type dynamometer is used to measure grip strength.

The site staff instructs the patient to adjust the grip width so that the second joint of the index finger is approximately 90 degrees (almost right angle).

The site staff asks the patient to be careful not to touch the body or clothes with hand while keeping arms down naturally. The site staff makes sure that the patient does not wave the grip dynamometer.

Grip strength is measured twice alternately left and right. Records are rounded down to the nearest kilogram and averaged for the better of the left and right.

10.2 CHAIR STAND TEST

Patients fold their arms across their chest and try to stand up once from a chair. If patients can stand from a chair, they repeat same action five times. It is measured the time required to perform five rise from a chair to an upright position as fast as possible without the use of arms.

[figure not shown]

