2.1.3 Secondary endpoint(s)

Secondary endpoints are the following safety endpoints:

- Change of muscle mass from baseline to Week 52
- Change of body fat measurement from baseline to Week 52
- Change of lean body mass from baseline to Week 52
- Change of total body water from baseline to Week 52
- Change of bone mineral content from baseline to Week 52
- Change of skeletal muscle index from baseline to Week 52
- Change of grip strength from baseline to Week 52
- Change of time in the 5-time chair stand test from baseline to Week 52

Please refer to Section [5.1.2](#), [5.1.3](#), and [5.1.4](#), and Appendix [10.1](#), [10.2](#), and [10.3](#) how each item will be measured and evaluated.

[figure not shown]

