3.3.3 Exclusion criteria

1. Uncontrolled hyperglycaemia with a fasting glucose level $>200 \text{ mg/dL}$ ($>11.1 \text{ mmol/L}$) during run-in period
2. Treatment with insulin within 12 weeks prior to informed consent
3. Impaired cognitive ability as supported by MMSE-J (defined as ≤ 23) and verified by the investigator at screening
4. Acute coronary syndrome (ST-elevation myocardial infarction [STEMI], non-STEMI, and unstable angina pectoris), stroke or transient ischemic attack within 12 weeks prior to informed consent
5. Indication of liver disease, defined by serum levels of either alanine aminotransferase (ALT [SGPT]), aspartate aminotransferase (AST [SGOT]), or alkaline phosphatase (ALP) above 3 x upper limit of normal (ULN) as determined during screening and run-in period
6. Impaired renal function, defined as eGFR $<45 \text{ mL/min/1.73 m}^2$ (severe renal impairment, Modification of Diet in Renal Disease [MDRD] formula) as determined during screening and run-in period
7. Low grip strength defined as $<28 \text{ kg}$ for male or as $<18 \text{ kg}$ for female at screening
8. Short length of calf circumference defined as $<34 \text{ cm}$ for male or 33 cm for female at screening
9. Inability to perform 5 times chair stand test according trial protocol
10. Already confirmed diagnose of sarcopenia (based on AWGS algorithm 2019)

² drug-naïve is defined as no antidiabetic drugs for at least 12 weeks prior to informed consent.

³ Menopause is a point in time 12 months after a woman's last period.

Proprietary confidential information © 2020 Boehringer Ingelheim International GmbH or one or more of its affiliated companies

11. Known history of diabetic ketoacidosis
12. Known contraindications to empagliflozin according to the Japanese label
13. Disorders causing haemolysis or unstable red blood cells
14. Any previous (within 2 years prior to informed consent) or planned bariatric surgery (or any other weight loss surgery) or other gastrointestinal surgery that induce chronic malabsorption
15. Medical history of cancer (except for resected non-invasive basal cell or squamous carcinoma) and/or treatment for cancer within the last 5 years
16. Treatment with anti-obesity drugs within 12 weeks prior to informed consent or any other treatment at the time of screening (i.e., surgery, aggressive diet regimen (e.g., low-carbohydrate diet), etc.) leading to unstable body weight

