6.6.3 Safety and other variables

Missing safety data will not be replaced.

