7.8.5 Others

Time curve analysis

Descriptive statistics will be presented in tables for creatinine, eGFR, haematocrit, haemoglobin and weight over time by treatment. Presented values will be used to create plots of the parameters over time.

In addition, tables of descriptive statistics for creatinine, eGFR values will also be presented for age subgroups.

Secondary endpoints analyses

Secondary endpoints in this trial only provide one post-baseline assessment (no repeated measurements). ANCOVA will be performed to compare the change from baseline in each of the continuous secondary endpoints at week 52 on the TS (OC-IR).

The statistical model will be: Change from baseline in secondary endpoint after 52 weeks = baseline secondary endpoint + age + sex + treatment + BMI + baseline HbA1c + random error.

In addition, descriptive statistics will be provided by visit including actual values and change from baseline values in the abovementioned secondary endpoints at Week 52. Descriptive statistics will also be presented with boxplots in each group both at baseline and at Week 52.

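### A patient who can no longer complete five chair stands at Week 52 has no time and leaves the ANCOVA; the plan should record and count these patients by arm

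*Protocol*

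**What the plan says.** Protocol 2.1.3 introduces its list with "Secondary endpoints are the following safety endpoints", and the last item is "Change of time in the 5-time chair stand test from baseline to Week 52". Appendix 10.2 first asks the patient to rise once, and then: "If patients can stand from a chair, they repeat same action five times". The outcome is a duration: "It is measured the time required to perform five rise from a chair to an upright position". The visible text gives no value, cap, code or category for a patient who cannot rise once, or who rises once but cannot finish five.

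Protocol 3.3.3 lists as an exclusion: "Inability to perform 5 times chair stand test according trial protocol".

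SAP 7.8.5 notes that the secondary endpoints have a single post-baseline assessment and states: "ANCOVA will be performed to compare the change from baseline in each of the continuous secondary endpoints at week 52". The analysis uses the treated set with observed cases, keeping values after rescue (OC-IR). SAP 6.6.3 adds: "Missing safety data will not be replaced". Protocol 7.3 likewise plans no imputation for safety evaluations.

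**The concern.** Chair stand time is in the trial to show whether lower-limb function declines. Protocol 1.1 raises the possibility that SGLT-2 inhibition breaks down muscle protein and leads to sarcopenia. Protocol 3.2 gives the lack of placebo-controlled data on lower limb function in the elderly as a reason for the design, and Protocol 5.1.3 treats the test as a measure for assessing sarcopenia.

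A patient who could do the test at entry and cannot at Week 52 because of lost function has one of the worst results that the test can give. The stated rules handle that result like a missed visit. The ANCOVA then describes only patients still able to perform, and nothing planned in the visible text shows how many were not. If inability differs between arms, part of the treatment difference lies in the patients who were removed.

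**Working it through.** **The path through the rules**

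1. All randomised patients can perform the test at entry (Protocol 3.3.3), so inability from lost function is a change from baseline.
2. A patient who cannot finish produces no time (Appendix 10.2).
3. There is one post-baseline assessment (SAP 7.8.5), so no other visit can contribute.
4. OC-IR (SAP 6.6.2.3) keeps values observed after rescue. It cannot supply a value that was never observed.
5. Missing safety data are not replaced (SAP 6.6.3, Protocol 7.3). The patient is therefore not in the ANCOVA.

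**The plan's own figure**

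The only sample size is for HbA1c (Protocol 7.5: difference 0.5%, SD 0.85%, two-sided 5%). It reproduces: 62 per group gives 90.1% power by the noncentral t, and 62 / 0.97 = 63.9, so 64 are randomised. It says nothing about the chair stand test, for which the documents give no mean, SD or failure rate. Everything below rests on assumptions.

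**Harm lying only in those who fail**

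Assume 62 per arm, change with mean 0 and SD 1.8 s in both arms among those able, and inability adding 10 s. Let p_E and p_P be the failure rates on empagliflozin and placebo.

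- Omitted difference = 10 × (p_E − p_P).
- Variance per arm with failures scored = 1.8² + 10² × p(1 − p).
- SE = √[(variance_E + variance_P) / 62].

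| p_E v p_P | Patients unable (62p) | Omitted difference | Variances | SE |
|---|---|---|---|---|
| 3% v 0% | 1.9 v 0 | 0.3 s | 6.15, 3.24 | 0.39 s |
| 5% v 1% | 3.1 v 0.6 | 0.4 s | 7.99, 4.23 | 0.44 s |
| 8% v 3% | 5.0 v 1.9 | 0.5 s | 10.60, 6.15 | 0.52 s |

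The ANCOVA on observed times has expectation 0.0 s in each row, because no effect was assumed among those able.

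A second set of assumptions (64 per arm, baseline mean 9 s and SD 2, change SD 2, failures 8 s worse, 3,000 simulated trials per row) shows how direction depends on the rates:

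| p_E v p_P | Difference, failures counted | Difference, failures dropped |
|---|---|---|
| 5% v 2% | 0.25 s | 0.00 s |
| 10% v 2% | 0.65 s | 0.00 s |
| 5% v 5% | 0.00 s | 0.00 s |
| 2% v 10% | −0.63 s | 0.00 s |

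With equal rates nothing is lost from the comparison. With more failures on placebo a benefit disappears.

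**Harm spread over all patients**

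Take the same distributions, a uniform slowing of 1.0 s on empagliflozin, and patients slower than 13, 15 or 18 s unable to finish. Failure rates are 14.5% v 7.9%, 3.9% v 1.7% and 0.2% v 0.1%. The estimate among those who finish is 0.85, 0.94 and 0.99 s, so most of the effect is still seen.

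**The case against.** A reader might infer that harm on this endpoint is understated outright. The documents do not support that. They give no failure rate, and the direction between arms depends on which arm has more failures.

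A reader might also infer that the omitted effect is as large as its standard error or larger, by setting 0.3 to 0.5 s against 1.8 × √(2/62) = 0.32 s. That standard error belongs to the data with failures removed. Scoring failures as 10 s worse also raises the variance, and the effect is then below its standard error in every row of the first table.

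Nor is there a good case for replacing the ANCOVA with a rank test. Under the first table's assumptions (4,000 simulated trials per row), a worst-rank Wilcoxon test rejects in 5.9%, 6.2% and 7.8% of trials, against 4.9%, 4.5% and 5.7% with failures dropped. That is little gain for losing the main estimate in seconds.

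The context also counts against a strong claim:

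- Secondary endpoints are exploratory (Protocol 7.1).
- Low grip strength, small calf circumference and confirmed sarcopenia are excluded as well as inability (Protocol 3.3.3), so failures may be rare.
- Grip strength, muscle mass and skeletal muscle index cover related ground. SAP 7.8.1.4 tabulates muscle weakness terms, and SAP 7 reports N with non-missing values, so unequal missingness would show.
- The figure in Appendix 10.2 is not shown, parts of the SAP are redacted, and the eCRF and site instructions are not in the documents. A recording rule may exist there.

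All of this limits the size and strength of the point. It does not remove it. The adverse event table depends on someone reporting an event, and Protocol 5.2.6.1.1 does not name functional tests among the findings to record. N shows that a value is missing, but not why.

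**Conclusion.** The point holds in a limited form. On the visible text, a patient who attends Week 52 and cannot complete the test because of lost function leaves the comparison, and no planned output reliably shows it. Mean worsening within each arm is understated whenever this happens. A harm between arms is understated only if inability is more frequent on empagliflozin.

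The plausible size is modest: 0.3 to 0.5 s omitted, with a standard error of 0.39 to 0.52 s, at assumed failure rates of 3% v 0% to 8% v 3%, a 10 s penalty and an SD of change of 1.8 s. Those rates mean about two to five patients unable on empagliflozin and none to two on placebo. If the slowing is shared by all patients, the planned analysis keeps most of it. The case for acting is that inability is a safety outcome in its own right, and that its cause may not be recoverable later if it is not recorded at the visit.

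**What to change.** 1. Keep the planned ANCOVA in SAP 7.8.5 as the main analysis, with its estimate in seconds.
2. Record 'unable to perform' at Week 52, with its reason, separately from tests missing for other reasons, if the eCRF does not already do so. The reason lets lost function be told apart from, for example, a fracture or acute illness.
3. Tabulate the number unable by arm. This is the most informative addition.
4. Prespecify a supportive analysis that gives patients unable to perform the worst rank, and state in the SAP which recorded reasons qualify.

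The cost is a small amount of eCRF and analysis work, and a supportive result that is not in seconds. The change does not help with patients who do not attend Week 52. They remain missing, and the report should say so beside the count.

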10.3 BODY COMPOSITION

Body composition is measured by using BIA (MC-780A-N, TANITA). The patient barefoot stands on the bench evenly on the toe and heel electrodes and holds the grip on each hand. Note: do not move during the measurement.

It is recommended that urination and defecation is completed before measurement. For a patient who has dehydration, hypothermia, swelling or fever, the visit to measure body composition has to be rescheduled as soon as possible.

[figure not shown]

[figure not shown]

[figure not shown]

11. DESCRIPTION OF GLOBAL AMENDMENT(S)

This is the original protocol.

11.1 GLOBAL AMENDMENT 1

Date of amendment	
EudraCT number	
EU number	
BI Trial number	
BI Investigational Medicinal Product(s)	
Title of protocol	
Global Amendment due to urgent safety reasons	
Global Amendment	
Section to be changed	
Description of change	
Rationale for change	

11.2 GLOBAL AMENDMENT 2

Date of amendment	
EudraCT number	
EU number	
BI Trial number	
BI Investigational Medicinal Product(s)	
Title of protocol	
Global Amendment due to urgent safety reasons	
Global Amendment	
Section to be changed	
Description of change	
Rationale for change	

2. LIST OF ABBREVIATIONS

Term	Definition / description
AE	Adverse event
AESI	Adverse event of special interest
ALT	Alanine transaminase
ANCOVA	Analysis of covariance
AST	Aspartate transaminase
ATC	Anatomical-Therapeutic-Chemical classification
BI	Boehringer Ingelheim
BIcMQ	BI-customized MedDRA query
BMI	Body mass index
CEC	Clinical event committee
CRF	Case report form
CT	Concomitant therapy
CTP	Clinical Trial Protocol
CTR	Clinical Trial Report
DBL	Database Lock
DBP	Diastolic blood pressure
DKA	Diabetic ketoacidosis
DM&SM	Boehringer Ingelheim Data Management and Statistics Manual
ECG	ECG Electrocardiogram
EDMS	Electronic Document Management System
eCRF	Electronic Case Report Form
eGFR	Estimated glomerular filtration rate
EMA	European medicines agency
EOT	End of treatment
EOS	End of study
FAS	Full analysis set
FPG	Fasting plasma glucose
HbA1c	Glycated haemoglobin
ICH	International Conference on Harmonisation
iPD	Important protocol deviation
IRT	Interactive response technology
ITT	Intention to treat
LLT	Lowest Level Term
LOCF	Last observation carried forward
MDRD	Modification of diet in renal disease

Term	Definition / description
MedDRA	Medical Dictionary for Regulatory Activities
[REDACTED]	[REDACTED]
MMRM	Mixed-effect Model Repeated Measures
[REDACTED]	[REDACTED]
MQRM	Medical Quality Review Meeting
NCF	Non-completers considered failure
OC	Observed case
OC-IR	Observed cases, including values after rescue
OR	Original results
PK	Pharmacokinetics
PPS	Per protocol set
PT	Preferred term
PD	Protocol deviation
Q1	Lower quartile
Q3	Upper quartile
REML	Restricted maximum likelihood
RS	Randomised set
SBP	Systolic blood pressure
SCR	Screened set
SD	Standard deviation
SDG	Standardized Drug Groupings
SMQ	Standardised MedDRA query
SOC	System Organ Class
TMF	Trial Master File
TOC	Table of contents
TS	Treated set
TSAP	Trial statistical analysis plan
ULN	Upper limit of normal
WHO	World Health Organisation

3. INTRODUCTION

As per ICH E9 ([1](#)), the purpose of this document is to provide a more technical and detailed elaboration of the principal features of the analysis described in the protocol, and to include detailed procedures for executing the statistical analysis of the primary and secondary variables and other data.

This TSAP assumes familiarity with the CTP, including Protocol Amendments. In particular, the TSAP is based on the planned analysis specification as written in the CTP Section 7 “Statistical Methods and Determination of Sample Size”. Therefore, TSAP readers may consult the CTP for more background information on the study, e.g., on study objectives, study design and population, treatments, definition of measurements and variables, planning of sample size, randomization.

SAS® Version 9.4 or a later version will be used for all analyses.

4. CHANGES IN THE PLANNED ANALYSIS OF THE STUDY

Descriptions in the CTP related to statistical analysis will be changed as follows:

- [REDACTED]
- [REDACTED]
- [REDACTED]
- Descriptive statistics on the impact of COVID-19 on study visits as well as trial medication intake will be provided if any.
- The definition of iPDs will be specified in the DV domain instead of the TSAP prior to DBL.

5. ENDPOINTS(S)

5.1 PRIMARY ENDPOINT(S)

The primary endpoint is defined in the CTP Section 2.1.2.

5.2 SECONDARY ENDPOINT(S)

5.2.1 Key secondary endpoint(s)

Not applicable.

5.2.2 Secondary endpoint(s)

Secondary endpoints are listed in the CTP Section 2.1.3.

